## 6.12 Sample Size

## 6.12.1 Younger Cohort 3 to <7 Years of Age

The study will have 90% power to reject two one-sided null hypotheses that one treatment group is >=0.75 logMAR lines better than the other in favor of an alternative hypothesis that the simultaneous and sequential treatment groups are equivalent with respect to change in VA, where "equivalent" is the 2 groups having mean change in amblyopic eye VA within <0.75 logMAR lines, as determined by statistical tests of:

**H**Null 1 = (Simultaneousmean change - Sequentialmean change) ≥ 0.75logMAR lines VA 1233 **H**Null 2 = (Sequentialmean change - Simultaneousmean change) ≥ 0.75logMAR lines VA

1235 Halternative 1 = 0 ≤ (Simultaneousmean change - Sequentialmean change) < 0.75logMAR lines VA

 1236 Halternative 2 = 0 ≤ (Sequentialmean change - Simultaneousmean change) < 0.75logMAR lines VA

The primary analysis will follow the intent-to-treat principle whereby all participants randomized will be included in the analysis.

## **6.12.1.1 Sequential Treatment**

To estimate the treatment effect for those randomized to sequential treatment, data from a previous PEDIG study, ATS5,  were used; the data used were limited to ATS5 participants who met the eligibility criteria for the current study (see Table 1).

One-hundred thirty-nine (139) participants aged 3 to 6 years with amblyopia due to anisometropia, strabismus, or both were treated with spectacles alone in a spectacles-only phase of the ATS5 study. Participants had visits every 5 weeks until amblyopia resolved (amblyopic eye VA same or better than best fellow-eye VA during study) or VA was stable (stable defined as <1 line improvement in logMAR VA between 2 subsequent 5-week visits). Upon completion of the spectacles-only phase, those with residual amblyopia were randomized to patching 2 hours per day/7 days per week or continued spectacles alone with visits every 5 weeks until VA was stable or amblyopia resolved.

The mean change in logMAR VA from the spectacle phase baseline visit to the visit of maximum VA in the ATS5 study is summarized in Table 1 below.

Table 1 – Visual Acuity Response in the ATS5 Study

Table 1 – Visual Acuity Response in the A	 185 Stuay	717,10	
		Change in logMA	
		Spectacle Phase	
		to Visit of Maximu	1
		Mean	SD
	N	(95% CI)	(95% CI)
Enrolled into Spectacle Phase*	139		
Dropped prior to stability or resolution	10	1.9 (1.1 to 2.7)	1.1 (0.8 to 1.9)
with spectacles			
Resolved in spectacle phase	28	4.3 (3.7 to 5.0)	1.7 (1.4 to 2.3)
Stable residual amblyopia;	46		
Randomized to Patching			
Completed RCT phase	45	3.8 (3.4 to 4.3)	1.5 (1.3 to 1.9)
Dropped prior to stability or	1	2.0	-
resolution in RCT phase			
Stable residual amblyopia;	55		
Randomized to Continued Spectacles			
Completed RCT phase	52	3.2 (2.8 to 3.7)	1.6 (1.4 to 2.0)
Dropped prior to stability or	3	2.7 (1.2 to 4.1)	0.6 (0.3 to 2.2)
resolution in RCT phase			
Overall – Including those Randomized	139	3.5 (3.2 to 3.8)	1.7 (1.5 to 1.9)
to Continued Spectacles*		Median (Range)	

		3 (0 to 8)	
Overall – Excluding those Randomized	84	3.7 (3.4 to 4.1)	1.7 (1.5 to 2.0)
to Continued Spectacles*		Median (Range)	
		3 (0 to 8)	

\* Meeting criteria for current study: age 3 to <7, 20/40 to 20/200 amblyopic eye visual acuity, age normal felloweye visual acuity, IOD >=3 lines, no prior amblyopia treatment including spectacles. SD=standard deviation.

After a median of 20 weeks of treatment with spectacles alone followed by patching (if needed), the mean change in VA at the study visit of maximum acuity was 3.7 logMAR lines (95% CI = 3.4 to 4.1 logMAR lines) with a standard deviation of 1.7 logMAR lines (95% CI = 1.5 to 1.9 logMAR lines).

Given the more stringent criteria for VA stability in the present study (3 visits at least 8 weeks apart with no improvement) compared to the previous study (2 visits at least 5 weeks apart with no improvement), we anticipate that the magnitude of VA improvement in the current study will be larger.

#### **6.12.1.2 Simultaneous Treatment**

There are few data in the literature to help us estimate the treatment effect in our study for those randomized to simultaneous treatment with spectacles and patching. Agervi et al compared treatment with simultaneous spectacles plus Bangerter filters with spectacle correction alone to treat anisometropic children with previously untreated amblyopia.

Sixty-six participants were randomized to treatment with spectacles alone (n=33) or spectacles plus Bangerter filters (n=33) and completed a visit 1-year post-randomization. Age ranged from 4 to 5 years of age. The median logMAR BCVA in the amblyopic eye in each group at baseline was 0.4 logMAR (20/50) with a median IOD of 3 lines in each group; 3 (9%) and 4 (12%) had severe amblyopia of 20/125 or worse. Table 2 summarizes the response to treatment after 1 year.

Table 2 – Visual Acuity Response after Spectacles Alone or Spectacles Plus Bangerter

		Lines Change in Amblyopic Eye at 1	
		Year	Time to Resolution
	N	Median (range)	Mean (range)
Spectacles Alone	33	4 lines (2 to 9)	3.9 months
			(0.5 to 13.3 months)
Spectacles Plus Bangerter	33	4 lines (2 to 8)	2.2 months
			(0.4 to 9.7 months)

The median and range of amblyopic eye improvement in the Agervi et al study is similar to that seen in the previous ATS5 study (4 logMAR lines vs 3.7 logMAR lines, respectively). Given that a lower proportion of participants in the Agervi study had severe amblyopia 20/125 or worse, compared with ATS5 (11% vs 19%), it is therefore reasonable to expect the two treatment regimens (sequential and simultaneous) are equivalent with respect to VA outcomes; hence, an equivalence design is proposed.

The standard deviation for improvement in the spectacles plus simultaneous patching treatment group is expected to be the same as seen in ATS5 (1.7 logMAR lines) given the similar ranges of improvement in the two studies.

## 

## **6.12.3** Choice of Equivalence Margin

The equivalence margin was determined by the Protocol Leads and the PEDIG Operations Committee, using clinical judgment, based on simulated distributions of VA improvement corresponding to a mean difference between 2 populations of 0.25, 0.50, 0.75 and 1.0 logMAR lines. We presented side-by-side histograms of the distributions illustrating the shift in the distribution for each mean, along with corresponding differences for clinically meaningful cut points, e.g., difference in percent improving 2 or more logMAR lines, or percent with final VA of 20/32 or better. The consensus was that if the difference in mean improvement between treatments was less than 0.75 logMAR lines, then the treatments would be considered equivalent.

## **6.12.4 Sample Size Estimation**

Based on previous data from ATS5 on sequential treatment (mean improvement of 3.7 logMAR lines) and data from Agervi et al (median improvement of 4 logMAR lines), we propose to design the present study to test whether the two treatments are equivalent, where equivalent is defined as a difference in mean improvement of less than 0.75 logMAR lines.

Assuming that the true difference in mean VA change between the two groups is 0 and assuming a pooled standard deviation of 1.7 logMAR lines, a total sample size of 272 participants (136 per group) has 90% power with a type I error rate of 2.5% to reject the null hypothesis of non-equivalence in favor of the alterative that simultaneous treatment is equivalent to sequential treatment (Table 3).

The percentage of participants lost to follow-up or withdrawn is expected to be small overall (10%) and equal between the two treatment groups. No adjustment to sample size has been made since outcome VA will be imputed for these participants (see *section 6.4*).

Table 3. Total Sample Size Estimates for a 2-Arm Study \*

SD of Change (LogMAR lines)	Treatment Group Difference in Mean VA Change from Baseline (logMAR lines) Equivalence Margin			
	<0.50	<0.75		
1.6	538	242		
1.7	606	272		
1.8	678	304		
1.9	756	338		

 \* The number of participants in cells represents the total number of participants required to reject a 2-sided null hypothesis that simultaneous treatment is not equivalent to sequential treatment by >=0.75 logMAR lines in favor of the alternative that simultaneous treatment is equivalent to sequential, with an equivalence margin of <0.75 logMAR lines; from 2 one sided T-tests with an alpha=0.025 and power 90% for a range of pooled SD of change in VA (logMAR lines).

A sample size of 272 participants for an equivalence study will have 90% power to reject a null hypothesis of no difference in favor of an alternative superiority hypothesis that there is a

- difference between groups, if the true difference between groups is as small as 0.67 logMAR lines of VA, with a type 1 error rate of 5%.
- 1334

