#### 6.4 Primary Efficacy Outcome – Distance Visual Acuity in Amblyopic Eye

902 903

904

The primary efficacy outcome will be mean change in amblyopic eye logMAR distance VA between randomization and completion of randomized treatment or at 56 weeks, whichever is earlier.

905 906 907

The outcome VA for each participant is defined as either of the following:

908 909 910

911

1. Amblyopic eye VA (calculated as mean of test and retest) at the last visit that was the basis for a "stable resolved" or "stable residual" determination (in the sequential group, stable residual amblyopia criteria can be reached only *after* patching has been instituted); or

912 913 914

915

2. 56-week visit amblyopic-eye VA (calculated as mean of test and retest) in those completing a 56-week visit without ever meeting criteria for "stable resolved" or "stable residual" amblyopia (if retest missing at 56 weeks, the single test value will be used).

The outcome VA for participants who never meet criteria for "stable resolved" or "stable residual" amblyopia and do not complete the 56-week visit, or receive non-randomized treatment for amblyopia prior to meeting criteria for "stable resolved" or "stable residual" amblyopia, will be imputed using multiple imputation based on amblyopic eye VA scores while on randomized treatment (using the mean of test and retest if done).

The primary analysis will follow the intent-to-treat (ITT) principle whereby all participants randomized will be included in the analysis according to the treatment group assigned at randomization. An analysis of covariance (ANCOVA) will be performed to compute the difference in mean change in amblyopic-eye distance VA (in logMAR lines) between the sequential and simultaneous treatment groups, adjusted for baseline amblyopic eye distance VA, and a 2-sided 95% confidence interval will be constructed on the treatment group difference. Equivalence of treatment groups will be declared if the upper and lower 95% CI limits are smaller (in absolute value) than the equivalence margin of 0.75 logMAR lines. Superiority of one treatment over the other will be declared if the upper and lower ends of the 95% CI exclude 0 difference.

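### The 90% power claim counts imputed outcomes as observed ones: with the protocol's own 10% loss, power is between about 86% and just under 90.4% on the stated inputs

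*Protocol*

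**What the plan says.** Protocol section 6.12.4 begins its sizing with "Assuming that the true difference in mean VA change between the two groups is 0". It takes a pooled SD of change of 1.7 lines and a margin of 0.75 lines, and concludes that "a total sample size of 272 participants (136 per group) has 90% power with a type I error rate of 2.5"%. The footnote to Table 3 specifies two one-sided t-tests at 0.025 each. This matches section 6.4: "Equivalence of treatment groups will be declared if the upper and lower 95% CI limits are smaller" in absolute value than the margin. Section 6.12.4 then expects 10% loss, equal between the groups, and continues: "No adjustment to sample size has been made since outcome VA will be imputed for these participants". It closes by claiming 90% power for superiority at a true difference of 0.67 lines.

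Section 6.4 makes multiple imputation the primary analysis. Missing outcomes are imputed from acuity measured while the child was on the assigned treatment.

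Two supporting statements come earlier. Section 6.12.1.1 gives the ATS5 result after spectacles and, if needed, patching as a mean of 3.7 lines with a "standard deviation of 1.7 logMAR lines (95% CI = 1.5 to 1.9 logMAR lines"). Section 6.12.1.2 says that the median and range in the trial of spectacles with or without Bangerter filters "is similar to that seen in the previous ATS5 study (4 logMAR lines vs 3.7 logMAR lines, respectively").

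**The concern.** The 90% is a complete-data figure: it needs essentially all 272 outcomes to be observed. The protocol itself expects about one in ten to be missing and treats imputation as a replacement for them. Multiple imputation widens the standard error precisely because the imputed values are uncertain. It protects the intention-to-treat population, not the sample size.

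At stake is how a failure to show equivalence would be read. A reader told that the design had 90% power would give such a result more weight than the design supports. The same holds for the superiority statement.

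The two planning statements matter less. One understates the upper uncertainty in the SD. The other makes two studies look more alike than Table 1 shows.

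**Working it through.** **Inputs.** From section 6.12.4: n = 136 per group, SD 1.7, margin 0.75, true difference 0, alpha 0.025 per side, 10% missing. The recovery and correlation values below are assumptions, because the protocol gives neither.

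**Reproducing the plan.** For two one-sided tests at true difference 0, the normal approximation is

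power = 2·Φ(margin/SE − 1.960) − 1, with SE = SD·√(2/n).

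- n = 136: SE = 1.7·√(2/136) = 0.2062; 0.75/0.2062 = 3.638; 2·Φ(1.678) − 1 = 90.7%.
- The exact t-based calculation gives 90.4%. The smallest exact total for 90% is 270, against 272 stated.
- The other Table 3 cells reproduce within 2 participants.

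The stated number is therefore correct for complete data, with almost nothing to spare.

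**10% missing, nothing recovered.** n = 136 × 0.9 = 122.4; SE = 0.2173; 0.75/0.2173 = 3.451; 2·Φ(1.491) − 1 = 86.4%. Exact: 86.1%.

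**10% missing, partial recovery.** If on-treatment acuity predicts the missing outcome with a given R², the variance rises by the factor 1 + (0.1/0.9)(1 − R²), and the effective n is 136 divided by that factor.

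| Assumed R² | Effective n per group | Exact power |
|---|---|---|
| 0 | 122.4 | 86.1% |
| 0.25 | 125.5 | 87.2% |
| 0.50 | 128.8 | 88.3% |
| 0.75 | 132.3 | 89.4% |
| 1 | 136 | 90.4% |

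To keep the 135 per group behind the exact 270, R² must be at least 1 − 9 × (136/135 − 1) = 0.93.

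**Baseline adjustment.** The ANCOVA in section 6.4 reduces the SD to 1.7·√(1 − r²), where r is the correlation between baseline and change. With r = 0.30 (R² about 0.10), SD = 1.62, and 122.4 per group gives 90.0%.

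**Superiority at 0.67 lines** (normal approximation).
- n = 136: 0.67/0.2062 = 3.250; Φ(3.250 − 1.960) = 90.1%, as stated.
- n = 122.4: 0.67/0.2173 = 3.083; Φ(3.083 − 1.960) = 86.9%.

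**SD interval.** The limits are s·√((n − 1)/χ²).
- s = 1.7, n = 84: 1.48 to 2.00.
- s = 1.7, n = 139: 1.52 to 1.93.

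The 3.7-line mean belongs to the 84-child row of Table 1, whose SD interval is 1.5 to 2.0. The 1.5 to 1.9 in the text is that of the 139-child row.

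**Median.** Table 1 gives the ATS5 median as 3 (range 0 to 8). The 3.7 set against a median of 4 is the ATS5 mean.

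**The case against.** The strongest reply is that 86% is only the lower end. Acuity is measured every 8 weeks, so imputation will recover something. The planned ANCOVA was not credited in the sizing, and a modest baseline correlation would restore 90%. Nor is the fraction of missing primary outcomes fixed at 10%. A child lost after a stable determination already has an outcome, and section 4.4 lets families return for week 56 only. In the other direction, section 6.4 also imputes for children given non-randomised treatment before a stable determination.

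All of this stands, and it is why the result is a range. It does not rescue the reason given. The baseline correlation is a separate argument that the protocol does not make, and imputation alone would need an R² of about 0.93.

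A reader might also infer that the misquoted figures cause the shortfall. They do not: the 272 uses SD 1.7, margin 0.75 and difference 0, and none of these is misquoted. Nor do the documents support reading 4 versus 3.7 as a true difference of 0.3 lines, or 4 versus 3 as a gap larger than the margin. Both set one study beside another with a different population and endpoint. Within the Bangerter-filter trial, Table 2 shows medians of 4 and 4. Section 6.12.5 also leaves interim monitoring to the SAP, which is not at hand.

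**Conclusion.** The point holds as a correction to a stated figure and its reason. On the protocol's own inputs, 272 randomised with 10% missing gives between about 86% and just under 90.4% power for equivalence, and as low as about 87% for superiority at 0.67 lines. The lower ends assume that imputation recovers nothing and take no credit for baseline adjustment. Reaching 90% needs either near-perfect imputation or a baseline-change correlation of about 0.30, and the protocol states neither. It would go too far to say that the trial delivers 86% or certainly misses its power.

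The SD interval and the mean labelled as a median are real but separate errors that leave the 272 untouched. Severity is minor to moderate: the equivalence rule rests on the confidence interval, whose width will show the precision actually achieved.

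**What to change.** In section 6.12.4, delete the sentence that justifies making no allowance by imputation. Keep 272 and state that it gives 90% power with complete outcomes and about 86% to 90% with 10% missing. Name the assumption behind any figure in that range: the R² of the imputation model, or a baseline-change correlation of about 0.30, marked as assumed. Qualify the superiority statement in the same way (about 87% to 90%).

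Separately, in section 6.12.1.1 change the SD interval to 1.5 to 2.0, to match the 84-child row of Table 1. In section 6.12.1.2, either compare medians (4 and 3) or label 3.7 as a mean. Optionally, note that at SD 2.0, the upper limit in Table 1, 136 per group gives about 74% power.

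The cost is a wording change and a slightly less favourable power statement. Enrolment, endpoint and decision rule do not change.

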## 1335 **6.12.5** Interim Analysis and Sample Size Re-estimation

- An interim monitoring plan will be developed in conjunction with the DSMC and will be detailed in the statistical analysis plan.
- 1338
- 1339 **6.12.6 Secondary HRQOL Outcomes**
- We will test the null hypothesis of no difference between groups in each HRQOL domain with
- an alternative hypothesis that the treatment groups differ. The false discovery rate (FDR) method
- will be used to control the FDR at 5% and to adjust p-values for multiplicity.

## 1343 6.13 Older Cohort 7 to <13 Years of Age

- Given the eligibility requirement of no prior amblyopia treatment, we expect to recruit fewer
- participants for the older cohort. The study will not be powered for a specific hypothesis test
- within the older cohort; rather an analysis of covariance (ANCOVA) will be performed to
- compute the mean logMAR change in amblyopic-eye VA for the sequential and simultaneous
- treatment groups, adjusted for baseline amblyopic eye VA, and a 95% confidence interval will be
- 1349 constructed on the treatment group difference.

1350 1351

The primary analysis will follow the intent-to-treat principle with outcome VA defined as in section 6.4.

1352 1353 1354

Table 4 summarizes the half-width of a 95% confidence interval for a treatment group difference for various pooled standard deviations and sample sizes.

1355 1356 1357

1358

Table 4. Half-width 95% Confidence Interval for Treatment Group Difference in Older Cohort for Various Sample Sizes

SD of Change (logMAR lines)	N=50	N=75	N=125	N=150
1.6	± 0.90*	± 0.73	± 0.56	± 0.51
1.7	± 0.95	± 0.78	± 0.60	± 0.55
1.8	± 1.01	± 0.82	± 0.63	± 0.58

- \* Number in cells represents the half-width 95% confidence interval for logMAR treatment group difference.
- 1359 1360

## **CHAPTER 7. Data Collection and Monitoring**

## 7.1 Case Report Forms and Other Data Collection

The main study data are collected on electronic case report forms (CRFs). When data are directly collected in electronic case report forms, this will be considered the source data. For any data points for which the eCRF is not considered source (e.g., lab results that are transcribed from a printed report into the eCRF), the original source documentation must be maintained in the participant's study chart or medical record. This source must be readily verifiable against the values entered into eCRF. Even where all study data are directly entered into the eCRFs at office visits, evidence of interaction with a live participant must be recorded (e.g., office note, visit record, etc.)

Electronic device data files are obtained from the study software and individual hardware components. These electronic device files are considered the primary source documentation. Each participating site will maintain appropriate medical and research records for this trial, in compliance with ICH E6 and regulatory and institutional requirements for the protection of confidentiality of participants.

## 7.2 Study Records Retention

Study documents should be retained for a minimum of 3 years after completion of the final grant reporting. These documents should be retained for a longer period, however, if required by local regulations. No records will be destroyed without the written consent of the sponsor, if applicable. It is the responsibility of the sponsor to inform the investigator when these documents no longer need to be retained.

## 7.3 Quality Assurance and Monitoring

Designated personnel from the Coordinating Center will be responsible for maintaining quality assurance (QA) and quality control (QC) systems to ensure that the clinical portion of the trial is conducted and data are generated, documented and reported in compliance with the protocol adhering to Good Clinical Practice (GCP) and the applicable regulatory requirements, as well as to ensure that the rights and wellbeing of trial participants are protected and that the reported trial data are accurate, complete, and verifiable. Adverse events will be prioritized for monitoring.

A risk-based monitoring (RBM) plan will be developed and revised as needed during the course of the study, consistent with the FDA "Guidance for Industry Oversight of Clinical Investigations — A Risk-Based Approach to Monitoring" (August 2013). This plan describes in detail who will conduct the monitoring, at what frequency monitoring will be done, at what level of detail monitoring will be performed, and the distribution of monitoring reports.

The data of most importance for monitoring at the site are participant eligibility and adverse events. Therefore, the RBM plan will focus on these areas. As much as possible, remote monitoring will be performed in real-time with on-site monitoring performed to evaluate the verity and completeness of the key site data.

#### Elements of the RBM may include:

• Qualification assessment, training, and certification for sites and site personnel

- Oversight of Institutional Review Board (IRB) coverage and informed consent procedures
   Central (remote) data monitoring: validation of data entry, data edits/audit trail, protocol
  - Central (remote) data monitoring: validation of data entry, data edits/audit trail, protocorreview of entered data and edits, statistical monitoring, study closeout
  - On-site monitoring (site visits): source data verification, site visit report
- Agent/Device accountability
  - Communications with site staff
  - Patient retention and visit completion
- Quality control reports

1410

1411

14131414

1416

1417

1419

1426 1427

1432

- Management of noncompliance
- Documenting monitoring activities
- Adverse event reporting and monitoring

Coordinating Center representatives or their designees may visit the study facilities at any time in order to maintain current and personal knowledge of the study through review of the records, comparison with source documents, observation and discussion of the conduct and progress of the study. The investigational site will provide direct access to all trial related sites, source data/documents, and reports for the purpose of monitoring and auditing by the sponsor, and inspection by local and regulatory authorities.

